### 4.3 Exclusion criteria

A potential subject who meets any of the following criteria will be excluded from participation in this study:

1. Any exacerbation within the month prior to the start of the study
2. Diagnosis of cystic fibrosis
3. Active allergic bronchopulmonary aspergillosis (ABPA)
4. Any oral, IV or inhaled antibiotics (except for macrolides) within 1 month prior to the start of the study
5. Any IV or IM corticosteroids or change in oral corticosteroids ( $>$  10 mg) within 1 month prior to the start of the study
6. Any change/start treatment regimens macrolides, hypertonic saline, inhaled mannitol or other mucolytics, corticosteroids within 1 month prior to the start of the study
7. Severe immunosuppression or active malignancy
8. Active tuberculosis
9. Chronic renal insufficiency (eGFR  $<$  30 ml/min)
10. Use of loopdiuretics, urea or mannitol
11. Earlier diagnosed hearing impairment, balance disorders or neuromuscular disorders

12. Serious active haemoptysis
13. Have received an investigational drug or device within 1 month prior to the start of the study
14. Serious or active medical or psychiatric illness
15. Pregnancy and child bearing
16. History of poor cooperation or non-compliance
17. Unable to use nebulizers
18. Allergic for tobramycin or NaCl 0.9%

#### **4.4 Sample size calculation**

The hypothesis is that prolonged treatment with tobramycin reduces the number of exacerbations per patient by 50%. This reduction seems clinically relevant and is based on the assumption that maintenance treatment with TIS OD as well as intermittent TIS BID is comparable to that of azithromycin treatment. This assumption is derived from the data of the BAT trial (placebo: mean 2,1 exacerbations (sd 1.6); azithromycin: mean 0,8 exacerbations (sd 1.1). The reduction in percentage is used for the determination of trial size.

We used a poisson regression model to determine group size. For type I error and type II error 0.05 and 0.2 were used respectively. The hypothesis will be tested two sided. With a baseline exacerbation rate of 2.1 in the placebo group and an expected response rate ratio of 0.5 with an exposure time of 1 year a total of 18 evaluable patients are required to be on each treatment arm.

With a drop-out percentage of 30% we must include totally 48 (24 patients per group) patients.

Due to unforeseen reasons we initially include two extra patients per group. But after the interim analysis three extra patients will be included in the study, because the drop-off percentage is higher as expected in advance. Reason for discontinuation of the study is the intensive treatment and cleaning schedule of the inhaled study medication. So, with a total of 58 patients (29 per group) with bronchiectasis, and not the initially 52 patients (26 per group), we expect to achieve the intended effect size.

## 5. TREATMENT OF SUBJECTS

### 5.1 Investigational product/treatment

#### Tobramycin inhalation solution (TIS)

This medication is used to treat people with cystic fibrosis (CF) and non-CF bronchiectasis who have a persistent lung infection with Gram-negative bacteria (*H. influenzae*, *Klebsiella spp*, *E. coli*, *P. aeruginosa*, *e.g.*). People with bronchiectasis often produce thick, sticky mucus that can plug up the tubes, ducts and passageways in the lungs. This can result in serious breathing problems and infections in the lungs. Tobramycin belongs to a class of drugs known as aminoglycoside antibiotics. Tobramycin inhalation solution works by stopping the growth of Gram-negative bacteria and *S. aureus* that commonly infects the lungs of people with bronchiectasis. This effect decreases lung infections and damage and helps to improve breathing.

#### Placebo: Sodium chloride inhalation solution 0.9% (NaCl 0.9%)

This medication is frequently used as a placebo. Each single-use plastic ampule contains sterile, non-pyrogenic, preservative-free sodium chloride. There is no bacteriostatic agent or other preservative added. Sodium chloride inhalation solution 0.9% is well tolerated and no severe adverse effects or side effects were recorded.

### 5.2 Use of co-intervention

All co-medications are allowed, except for any oral (except for macrolides), IV or inhaled antibiotics within 1 month prior to the start of the study and any IV or IM corticosteroids or change in oral corticosteroids (> 10 mg) within 1 month prior to the start of the study. Immunosuppressive agents such as azathioprine, chemotherapeutic agents, and TNF $\alpha$  inhibitors are prohibited. Also, any change/start treatment regimens of macrolides, hypertonic saline, inhaled mannitol or other mucolytics, within 1 month prior to the start of the study are prohibited. Also, the use of loopdiuretics, mannitol or urea are prohibited.

### 5.3 Escape medication

In consultation with the own GP or respiratory physician the patient may use extra bronchodilators for relief of dyspnoea. In subjects who experience a pulmonary exacerbation, every effort should be made to continue their allocated inhaled study drug, unless the study drug is not tolerated, or the pulmonary exacerbation is believed to be related to study drug. All subjects who receive any study drug need to complete the visit 7 assessments. Subjects who are prematurely withdrawn from study drug will be encouraged to remain in the study and attend subsequent study visits; at a minimum, they should complete the visit 7 assessments as an early termination visit.

## 6. INVESTIGATIONAL PRODUCT

### 6.1 Name and description of investigational product(s)

#### Tobramycin Inhalation Solution USP

This medication is used to treat people with (CF) and non-CF bronchiectasis who have a persistent lung infection with Gram-negative bacteria (e.g., *H.influenzae*, *Klebsiella spp*, *E.coli*, *P. aeruginosa*). People with bronchiectasis often produce thick, sticky mucus that can plug up the tubes, ducts and passageways in the lungs. This can result in serious breathing problems and infections in the lungs. Tobramycin belongs to a class of drugs known as aminoglycoside antibiotics. Tobramycin inhalation solution works by stopping the growth of a Gram-negative bacteria and *S. aureus* that commonly infects the lungs of people with bronchiectasis. This effect decreases lung infections and damage and helps to improve breathing.

#### Sodium chloride inhalation solution 0.9% (NaCl 0.9%)

This medication is frequently used as a placebo. Each single-use plastic ampule contains sterile, non-pyrogenic, preservative-free sodium chloride. There is no bacteriostatic agent or other preservative added. Sodium chloride inhalation solution 0.9% is well tolerated and no severe adverse effects or side effects were recorded.

### 6.2 Summary of findings from non-clinical studies

#### 6.2.1 Pharmacokinetics

Tobramycin inhalation solution contains tobramycin, a cationic polar molecule that does not readily cross epithelial membranes. The bioavailability of tobramycin inhalation solution may vary because of individual differences in nebulizer performance and airway pathology. Following administration of tobramycin inhalation solution, tobramycin remains concentrated primarily in the airways.

#### 6.2.2 Sputum Concentrations

Ten minutes after inhalation of the first 300 mg dose of tobramycin inhalation solution, the average concentration of tobramycin was 1237 mcg/g (ranging from 35 to 7417 mcg/g) in sputum^37.

Tobramycin does not accumulate in sputum; after 20 weeks of therapy with the tobramycin inhalation solution regimen, the average concentration of tobramycin at ten minutes after inhalation was 1154 mcg/g (ranging from 39 to 8085 mcg/g) in sputum. High variability of tobramycin concentration in sputum was observed. Two hours after inhalation, sputum concentrations declined to approximately 14% of tobramycin levels at ten minutes after inhalation.

#### 6.2.3 Serum concentrations

The average serum concentration of tobramycin one hour after inhalation of a single 300 mg dose of tobramycin inhalation solution by cystic fibrosis patients was 0.95 mcg/mL. After 20 weeks of therapy

on the tobramycin inhalation solution regimen, the average serum tobramycin concentration one hour after dosing was 1.05 mcg/mL.

### 6.2.4 Elimination

The elimination half-life of tobramycin from serum is approximately 2 hours after intravenous (IV) administration. Assuming tobramycin absorbed following inhalation behaves similarly to tobramycin following IV administration, systemically absorbed tobramycin is eliminated principally by glomerular filtration. Unabsorbed tobramycin, following tobramycin inhalation solution administration, is probably eliminated primarily in expectorated sputum.

### 6.3 Summary of findings from clinical studies

In present table all studies using TIS (all preparations) and outcomes are documented.

Study	Design	Number of subjects	Therapy given	Outcomes
Orriols et al., 1999	RCT PG	15 completed, 7 on active treatment	Aerosol ceftaz and tobra for 12 months	Significantly fewer admissions in the active group. Decrease in FEV 1 while on active therapy compared with placebo ( $p = NS$ )
Barker et al., 2000;  Couch, 2001  NB: same study was reported twice	RCT	74: 37 TSI 37 placebo	TSI or placebo 4 weeks	Decrease in P.a. density on TSI but 11% developed P.a. resistance. Improved "general health" Decrease in FEV 1 while on TSI compared with placebo ( $p = NS$ ) and 32% developed dyspnea on TSI.
Drobnic, et al., 2005 	RCT COT	30: 20 finished 5 died	6 months of TSI or placebo then cross after 1 month washout	Decrease in FEV 1 while on TSI compared with placebo ( $p = NS$ ) No change in antibiotic use or QOL 10% of subjects had bronchospasm while on TSI.
Scheinberg and Shore, 2005 	OLT	41	3 × 14 days On and off cycles	Eradication of Pa in 22% and resistance developed in 7%. Nine withdrawals due to cough and wheezing.
Bilton et al., 2006 	RCT PG	53 enrolled 43 finished	TSI added to ciprofloxacin vs. cipro alone for 14 days	Significant decrease of P.a. in sputum. Decrease in FEV 1 while on TSI compared with placebo ( $p = NS$ ). 50% on TSI developed wheeze vs. 15% on placebo.

All studies used tobramycin solution for inhalation (TSI) 300 mg b.i.d. as active drug except Orriols used aerosol ceftazidime 1 g every 12 h and tobramycin injection solution 100 mg every 12 h. Abbreviations: PG, parallel group trial; RCT, randomized controlled trial; OLT, open label trial; COT, crossover trial, NS, not significant; P.a., *Pseudomonas aeruginosa*; SGRQ, St George Respiratory Questionnaire; ceftz, ceftazidime; tobra, tobramycin; TSI, tobramycin solution for inhalation.

TIS USP (TEVA) has only been studied in CF patients (two studies, unpublished). In each study, tobramycin inhalation solution therapy resulted in a significant reduction in the number of *P.*

*aeruginosa* colony forming units (CFUs) in sputum during the on-drug periods. Sputum bacterial density returned to baseline during the off-drug periods. Reductions in sputum bacterial density were smaller in each successive cycle. Patients treated with longterm tobramycin inhalation solution were hospitalized for an average of 5.1 days compared to 8.1 days for placebo patients. Patients treated with tobramycin inhalation solution required an average of 9.6 days of parenteral anti-pseudomonas antibiotic treatment compared to 14.1 days for placebo patients. During the 6 months of treatment, 40% of tobramycin inhalation solution patients and 53% of placebo patients were treated with parenteral anti-pseudomonas antibiotics.

The relationship between in-vitro susceptibility test results and clinical outcome with tobramycin inhalation solution therapy is not clear. However, 4 tobramycin inhalation solution patients who began the clinical trial with *P. aeruginosa* isolates having MIC values  $\geq 128$  mcg/mL did not experience an improvement in FEV1 or a decrease in sputum bacterial density.

Treatment with longterm tobramycin inhalation solution did not affect the susceptibility of the majority of *P. aeruginosa* isolates during the 6-month studies. However, some *P. aeruginosa* isolates did exhibit increased tobramycin MICs. The percentage of patients with *P. aeruginosa* isolates with tobramycin MICs  $\geq 16$  mcg/mL was 13% at the beginning, and 23% at the end of 6 months of the tobramycin inhalation solution regimen.

#### **6.4 Summary of known and potential risks and benefits**

Maintenance use of TIS UPS is generally well tolerated as shown during two clinical studies in 258 cystic fibrosis patients ranging in age from 6 to 48 years. Patients received tobramycin inhalation solution in alternating periods of 28 days on and 28 days off drug in addition to their standard cystic fibrosis therapy for a total of 24 weeks. No severe adverse effects were recorded. The most common side effects are coughing, sore throat, dysphonia and bronchospasm. Tinnitus (3%) was transient, resolved without discontinuation of the tobramycin inhalation solution treatment regimen, and were not associated with loss of hearing in audiograms.

Nine (3%) patients in the tobramycin inhalation solution group and nine (3%) patients in the placebo group had increases in serum creatinine of at least 50% over baseline. In all nine patients in the tobramycin inhalation solution group, creatinine decreased at the next visit.

#### **6.5 Description and justification of route of administration and dosage**

TIS UPS is produced and packed by TEVA Pharmaceuticals in accordance to the principles and the detailed guidelines of Good Manufacturing Practice for Medicinal Products and will be delivered at the pharmacy of Stichting Haarlemse Ziekenhuizen. All the public information about the investigational product is written in the SPC-document. TIS is packaged in small plastic ampules (miniplasco's) of 5 ml; each ampule contains one full dose of tobramycin (300mg). These ampules are packed in identical sealed boxes. The investigators will be blinded for the content of the boxes. The placebo is a plastic ampule of NaCl 0.9% 5ml. These ampules are also called miniplasco's. The placebo is produced by Centrafarm B.V in accordance to the principles and detailed guidelines of Good Manufacturing

Practice for Medical Products. Also, these ampules will be delivered at the pharmacy of Haarlemse Ziekenhuizen. The shape of the ampules of the placebo (NaCl 0.9%) is different from the ampules of TIS, therefore the ampules will be packed in identical sealed boxes. The investigators will be blinded for the content of the boxes, in this way the blind will remain existent.

Labelling will be done at the pharmacy of Haarlemse Ziekenhuizen. The ampules remain intact, and a new label is printed on the package in accordance with the guidelines Good Manufacturing Practice. The expiration date, reference code and batch code are printed on the ampules and sealed boxes. The 300mg dose of tobramycin inhalation solution (or placebo) is the same for patients regardless of age or weight. Doses should be inhaled as close to 12 hours apart as possible and not less than 6 hours apart. In this study TIS is used once daily in the morning. The pharmacy of Haarlemse Ziekenhuizen is responsible for the labelling and packaging of the sealed boxes for both TIS and placebo. These labelled and sealed boxes are sent to the pharmacy of the Noordwest Ziekenhuisgroep, location Alkmaar. The transportation is under refrigeration at 2-8°C/36-46°F. The storage of the investigational product (TIS or placebo) is under refrigeration at 2-8°C/36-46°F with 2-year shelf life at these circumstances. Temperature will be monitored continuously.

Upon removal from the refrigerator, tobramycin inhalation solution USP pouches (opened or unopened) may be stored at room temperature (up to 25°C/77°F) for up to 28 days. Tobramycin inhalation solution USP should not be used beyond the expiration date stamped (totally of two years) on the ampule when stored under refrigeration (2-8°C/36-46°F) or beyond 28 days when stored at room temperature (25°C/77°F). TIS USP ampules should not be exposed to intense light. The solution in the ampule is transparent but may darken with age if not stored in the refrigerator; however, the color change does not indicate any change in the quality of the product

The investigational product (TIS or placebo) is especially formulated to be used with an InnoSpire Deluxe compressor (Philips Respironics) with a SideSteam Plus nebulizer with mouthpiece. This compressor is produced by Philips Respironics and delivered by Mediq Romedic Netherlands. The air compressor is used with a nebulizer to turn the medicine into a fine spray. Before inhalation of TIS salbutamol is administered at a dose of 200mcg to prevent bronchial constriction. TIS (or placebo) while breathing through the mouthpiece the spray is inhaled into the airways. The nebulizer is used for about 5 minutes. The whole procedure; preparation of the nebulizer, inhalation and cleaning takes about 15 minutes to complete. Afterwards the patient should rinse their mouth three times.

## **6.6 Dosages, dosage modifications and method of administration**

See 6.5

## **6.7 Preparation and labelling of Investigational Medicinal Product**

Randomisation will be done by the statistician at the Noordwest Ziekenhuisgroep. The randomisation list will be sent to the pharmacy of Haarlemse Ziekenhuizen. Labelling takes place at the pharmacy of the Haarlemse Ziekenhuizen in accordance to this randomisation list. This labelled and sealed boxes

are sent to the pharmacy of the Noordwest Ziekenhuisgroep. Storage will be done in the refrigerator at the department of pulmonology in accordance to the GCP guidelines. See also 6.5.

## **6.8 Drug accountability**

Medication will be provided by TEVA Pharmaceuticals and delivered at the pharmacy of the Haarlemse Ziekenhuizen. After labelling and packaging, the investigational medication will be delivered at the pharmacy of the Noordwest Ziekenhuisgroep location Alkmaar. All medication is coded. The medication will be delivered by the investigator at all participating centres. Transportation will be at refrigeration at 2-8°C/36-46°F in special boxes. The medication will be stored at the participating centres under refrigeration at 2-8°C/36-46°F, according to the local arrangements. Medication will be provided at the patients during each out-patient visit, with the explanation to store the investigational product in the refrigerator at 2-8°C/36-46°F. Used ampules are returned in opaque sealed plastic bags during the out-patient visit. The used ampules are counted by an independent research nurse and will be recorded in an excel file. In this way the blind will remain existent and nevertheless compliance can be checked. The ampules will be destroyed by the local pharmacy of the relevant hospital.

## **7. METHODS**

### **7.1 Study parameters/endpoints**

#### **7.1.1 Main study parameter/endpoint**

The primary objective of the study is to determine whether maintenance use of TIS once daily (OD) as compared to placebo may reduce the number of exacerbations per year in patients with non-CF bronchiectasis.

#### **7.1.2 Secondary study parameters/endpoints (if applicable)**

The secondary objective of this study is to evaluate the effect of TIS treatment on time to next exacerbation, airflow limitation (FVC% predicted, FEV1% predicted), LRTI-VAS, Quality of Life-Bronchiectasis (QOL-B), Leicester cough score, bacterial load in sputum and tobramycin resistance, including MIC values, depending on the capabilities of the microbiological laboratory.

#### **7.1.3 Other study parameters (if applicable)**

Other objectives of the study are age of the patients, sex, tobacco and alcohol use, number of patients with COPD or other etiologies, and the biomarkers like C-reactive protein level and leukocytes in serum, liver function and renal function. In addition to these objectives, it is also interesting how much patients withdrew from the study because of bronchospasm or other adverse effects, supplementary use of oral antibiotics due to an exacerbation, azithromycin maintenance and pseudomonas carriage. An exacerbation will be noticed by using the diary card weekly. If there are any changes in medical

condition and compliance with medication, this will be noticed by using the diary card. In subjects who experience a pulmonary exacerbation, the own GP or respiratory physician will assess the severity of pulmonary symptoms and signs and prescribes antibiotics and/or medication (e.g. prednisolone, bronchodilators). If so, the investigator will be informed. At least also an objective of the study is hospitalization and duration of the hospitalization.

## **7.2 Randomisation, blinding and treatment allocation**

Randomisation will be done by Excel and SPSS statistics 20 with an allocation ratio of 1:1 between groups. Once a number is assigned to a patient, the investigator will open the treatment regimen assignment and the subject will receive treatment according to the assigned strategy. The numbers are anonymous dispensed in closed envelopes and stored at department of pulmonary diseases of the Noordwest Ziekenhuisgroep location Alkmaar. The main-investigator will be responsible for maintaining the storage and allocation of the envelopes.

## **7.3 Study procedures**

Patients with bronchiectasis and who fulfil the inclusion and exclusion criteria will be asked to participate in the study. After a run-in period of 4 weeks' patients will be randomized to receive one of the two possible treatment regimens: TIS OD 300 mg daily or placebo. Administration will be continuous for the full 12 months. According to the parallel group design patients will be treated for 52 weeks. After completing the intervention period patients will have a follow-up (wash out period) of 4 weeks. This wash-out period was considered to be one month, in which time the antimicrobial effect of the antibiotic supposedly disappears, as suggested in earlier studies.

Subjects will be evaluated at run-in = visit 0 (week -4), visit 1 (day 1- start of the study), visit 2 (week 13), visit 3 (week 26), visit 4 (week 39), visit 5 (week 52: end of treatment) and visit 6 (run-out; week 56: end of the study). One week after start of treatment a phone call will be scheduled. Clinical, laboratory, and bacteriology evaluations will be determined according to the schedule (Figure 1: study schedule). Subjects who terminate treatment should be followed for the same period as those who complete the study, according to the study schedule.

During the study any changes in medical condition and compliance with medication will be filed in the diary card.

At visit 1, after randomisation, a tolerance test with either TIS or placebo (blinded according to randomisation) will be performed. Before nebulizing TIS patients are treated with salbutamol 200mcg using an AeroChamber. During tidal breathing patients inhale 300mg TIS or placebo (at room temperature) by using the Innospire Deluxe nebulizer with mouthpiece during approximately 5 minutes. If patients develop a moderate-severe bronchial obstruction, patients are excluded from the study. The severity of bronchial obstruction and coughing is assessed by a specialized nurse, the respiratory physician or the own GP. An exacerbation is defined as the presence of three or more of the following symptoms or signs for at least 24 hours: increased cough, increased sputum volume, increased sputum purulence, haemoptysis, increased dyspnoea, increased wheezing, fever (>38.5°C)

or malaise, and the treating physician agreed that antibiotic and/or prednisolone therapy was required.

All participants are provided with 24-hour contact details (phone and mail) and invited to contact their respiratory physician or general practitioner and study staff at any time (including after hours) in the event of exacerbation symptoms, to ensure that these symptoms are evaluated prospectively.

Participants will be instructed to ensure that antibiotic prescriptions will be provided by the own respiratory physician of the centres or the general practitioner.

Criteria for protocol-defined pulmonary exacerbation (PDPE) will be adjudicated prospectively by the treating respiratory physician. Antibiotic and/ or prednisolone prescriptions are also directed by the treating respiratory physician or the general practitioner, and standardized according to microbiology and antibiotic tolerance. Deteriorations in respiratory symptoms that do not meet criteria for PDPEs will be termed non-protocol-defined PEs (non-PDPEs). In these circumstances, participants were advised that they did not require antibiotics and only if clinically indicated, determined by the treating physician or the general practitioner.

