#### **Day 1 (Visit 1)**

- Record medical history
- Assessment of LRTI-VAS
- Quality of Life-Bronchiectasis (QOL-B) questionnaire
- Leicester cough score
- Physical examination (including sputum characteristics, cough, dyspnoea, pleuritic chest pain, chills or rigors, and lung sounds) and vital signs (respiratory rate, heart rate, blood pressure, body temperature and oxygen saturation)

- Collection of demographic information, concurrent disease, concomitant medication use, and previous course(s) of antibiotic therapy in the preceding year
- Spirometry according to the standard criteria of the European Respiratory Society
- Concomitant medication monitoring
- Study drug and Innospire deluxe dispensation
- Inhalation tolerance test with either TIS or placebo (depending on randomisation) and first dose of study drug administered under supervision of study staff
- Instructions on proper administration and return of study drug and proper care of the nebulizer
- Diary card instruction

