### **7.6 Follow-up of subjects withdrawn from treatment**

Follow-up of patients withdrawn from treatment have an out-patient visit following the study schedule. These patients will be evaluated the same as the patients who complete the study. Subjects will be evaluated at run-in = visit 0 (week -4), visit 1 (day 1- start of the study), visit 2 (week 13), visit 3 (week 26), visit 4 (week 39), visit 5 (week 52: end of treatment) and visit 6 (run-out; week 56: end of the study). One week after start of treatment a phone call will be scheduled. During an exacerbation the patient will contact his/her own GP or specialist.

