#### **9.3.2 Modified Intent-To-Treat analysis (mITT)**

The patients who are randomised but dropped out from the study directly after the tolerance test due to a moderate-severe bronchial obstruction or a severe cough, are excluded from the mITT analysis. So the mITT population includes the patients who passed the tolerance test with TIS or placebo according to the randomisation.

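### Section 7.3 removes from the study patients who fail a post-randomisation tolerance test, which contradicts the follow-up rules and the all-randomised ITT analysis; if followed, the ITT rate ratio is the mITT rate ratio

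*Combined protocol and SAP*

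**What the plan says.** Section 7.3 places the test at visit 1: "At visit 1, after randomisation, a tolerance test with either TIS or placebo (blinded according to randomisation) will be performed". On failure it says: "If patients develop a moderate-severe bronchial obstruction, patients are excluded from the study". The visit 1 list pairs the test with the first supervised dose: "Inhalation tolerance test with either TIS or placebo (depending on randomisation) and first dose of study drug administered under supervision of study staff". A failure is therefore a randomised, dosed patient who stops treatment.

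Section 9.3.2 confirms the literal reading. The mITT set leaves out those who "dropped out from the study directly after the tolerance test due to a moderate-severe bronchial obstruction or a severe cough".

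Other sections ask for the opposite:

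- Section 7.3: "Subjects who terminate treatment should be followed for the same period as those who complete the study, according to the study schedule".
- Section 7.6, on patients withdrawn from treatment: "These patients will be evaluated the same as the patients who complete the study".
- Sections 3 and 5.3 require final assessments from everyone who received any study drug. Those withdrawn from drug "will be encouraged to remain in the study and attend subsequent study visits; at a minimum, they should complete the visit 7 assessments".
- Section 9.3.1 puts all randomised patients in the ITT population, and 9.4.1 makes intent-to-treat the analysis basis.

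Section 9.4.3 analyses the primary endpoint with a Poisson model of events over person-time, corrected for overdispersion. No section exempts tolerance-test failures from the follow-up rules, and none says how a patient with almost no follow-up enters the ITT analysis.

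**The concern.** A site cannot both exclude a patient from the study on day 1 and follow that patient to week 52. If it does the first, the all-randomised analysis exists in name only for the primary endpoint, because the data it needs are not collected.

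The set that remains is conditioned on response to the assigned product. A patient who reacts only to tobramycin can be detected and removed only in the TIS arm; the same kind of patient on placebo stays in. The arms are then no longer the groups that were randomised. How much this matters depends on how many such patients there are and how often they exacerbate.

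**Working it through.** **1. The plan's own figure.** Inputs from 4.4 and 9.1: placebo rate 2.1 per year, ratio 0.50, exposure 1 year, two-sided alpha 0.05, power 0.80, phi = 1, 1:1 allocation. With N the total:

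N = phi × (1.960 × √4 + 0.8416 × √(2 + 2/RR))² / (2.1 × (ln RR)²)

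At RR = 0.50 this gives 35.5, rounded up to 36, as the plan states. The same formula is used for power in step 6.

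**2. What an excluded patient contributes.** Zero events and about 1/365 year. In simulation (29 per arm, five null covariates, 1,200 runs per scenario) the nominal ITT and mITT log rate ratios never differed by more than 0.007. The equality holds for the estimate only. Near-empty records add residual degrees of freedom but almost no Pearson chi-square, so the nominal ITT standard error was 0.97 of the mITT one with 10% failing on TIS and 0.94 with 20%.

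**3. Apparent ratio with no drug effect.** Let f be the share of patients who would fail on TIS but pass on placebo, and k their exacerbation rate relative to the others. Both are assumed. The placebo arm keeps them, so its mean is 1 − f + f·k; the TIS arm loses them, so its mean is 1. Ratio = 1/(1 − f + f·k).

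| f | k = 0.75 | k = 1 | k = 1.5 | k = 2 |
|---|---|---|---|---|
| 5% | 1.01 | 1.00 | 0.98 | 0.95 |
| 10% | 1.03 | 1.00 | 0.95 | 0.91 |
| 20% | 1.05 | 1.00 | 0.91 | 0.83 |

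With all patients followed, the ratio is 1.00 throughout.

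**4. False-positive rate.** Simulated with 29 per arm, mean 2.1, phi = 1 and an overdispersion-corrected Wald test without covariates (100,000 trials). With failures followed it is about 5.4%. With failures excluded at f = 10% it is 5.6%, 5.3%, 5.9% and 7.6% for k = 0.75, 1, 1.5 and 2. At f = 20% it is 7.7% for k = 1.5 and 12.8% for k = 2.

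**5. Does imputing the placebo rate repair it?** Give the lost TIS patients the placebo-arm mean: ratio = (1 − f + f × (1 − f + f·k))/(1 − f + f·k). At f = 10%, k = 2: (0.90 + 0.10 × 1.10)/1.10 = 0.918, against 0.909 unimputed. At f = 20%, k = 2: (0.80 + 0.20 × 1.20)/1.20 = 0.867, against 0.833. It barely moves, because this imputation assumes that failures are average (k = 1).

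**6. Cost of following everyone.** Suppose the planned 0.50 holds in patients who tolerate TIS, and failures have no drug effect after stopping. Followed ratio = (0.50 × (1 − f) + f·k)/(1 − f + f·k).

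- f = 10%: 0.55 (k = 1); (0.45 + 0.20)/1.10 = 0.59 (k = 2).
- f = 20%: 0.60 (k = 1); (0.40 + 0.40)/1.20 = 0.67 (k = 2).

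Power from the step 1 formula. The value phi = 1.35 is an assumed middle value between 1.6²/2.1 = 1.22 and 1.1²/0.8 = 1.51, from the standard deviations in 9.1. The last two columns take 30% drop-out as contributing nothing (N = 58 × 0.7 = 40.6).

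| Ratio | N = 58, phi 1 | N = 58, phi 1.35 | N = 40.6, phi 1 | N = 40.6, phi 1.35 |
|---|---|---|---|---|
| 0.50 | 94% | 86% | 84% | 74% |
| 0.55 | 87% | 77% | 75% | 64% |
| 0.59 | 79% | 68% | 66% | 54% |
| 0.67 | 60% | 49% | 47% | 38% |

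These figures are somewhat optimistic: a simulated Wald test at 0.55 with 29 per arm fully followed gave 79% (phi = 1) and 67% (phi = 1.35).

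**The case against.** The strongest reply is that ITT is already defined correctly and mITT separately, and that exclusion may simply mean stopping study drug. The definition is indeed right; what is missing is the data. If stopping drug was meant, one sentence settles the matter, but neither 7.3 nor 9.3.2 says so, and 9.3.2 points the other way.

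A second reply is that harm is not shown, and this stands. A reader might infer that the exclusion makes tobramycin look better than it is. The documents do not support that. Bias needs unequal failure by arm and a different exacerbation rate in failures, and neither figure is given. With k below 1 the direction reverses. The airway events tabulated in 6.3 (10% bronchospasm in one study, 50% against 15% wheeze in another) come from longer twice-daily use, not from a single supervised dose. They make unequal failure plausible and no more. The false-positive rate at f = 10% hardly moves unless k is near 2.

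A third reply is that some exacerbations of excluded patients may appear in medical records, since the definition requires a physician's decision to treat. That is possible, but the plan does not provide for collecting them.

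Finally, 7.1.3 already lists withdrawals because of bronchospasm or other adverse effects. That is correct; only a split of test failures by arm is missing.

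**Conclusion.** The contradiction is in the current text and should be fixed. Sections 7.3 and 9.3.2 take test failures out of the study, while 7.3, 7.6, 3, 5.3, 9.3.1 and 9.4.1 keep them in follow-up and in the analysis. Followed as written, the exclusion makes the ITT point estimate the mITT point estimate, with a slightly too small standard error under the ITT label.

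The possible distortion ranges from none (k = 1) to an apparent ratio of 0.91 at f = 10% or 0.83 at f = 20% (k = 2) with no drug effect. It rests wholly on assumed f and k, so it is a risk the design leaves open and not a demonstrated bias.

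A smaller mismatch belongs to the same point. Section 7.3 has both symptoms judged ("The severity of bronchial obstruction and coughing is assessed by a specialized nurse, the respiratory physician or the own GP") but names only obstruction as the ground for exclusion, whereas 9.3.2 also names severe cough.

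**What to change.** Reconcile 7.3 and 9.3.2 with 7.3's own follow-up rule, 7.6 and 9.3.1. The clinical criterion for stopping study drug is left to the sponsor.

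- State that patients who fail the test remain in study follow-up on the 7.6 schedule, with exacerbations recorded to week 52 whether or not they are on study drug, unless they decline.
- Reconcile the visit 7 named in sections 3 and 5.3 with the schedule in 7.3 and 7.6, which ends at visit 6.
- In 9.4.3, name ITT (all randomised) as primary and mITT as supportive.
- Split the withdrawals listed in 7.1.3 by arm for tolerance-test failures.
- For anyone already lost on day 1, run a sensitivity analysis over a range of k, for example 0.75 to 2, and not a single imputation at the placebo rate.
- Align the obstruction and cough wording of 7.3 and 9.3.2.

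The cost is wording plus follow-up of a few patients: 29 × 0.10 = 2.9, about 3 TIS patients at f = 10%, and any placebo failures. The real price is the dilution in step 6. It should be weighed under the same f and k as the benefit: where exclusion would distort most (k = 2), the loss of power is also largest.
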